The following should be taken into consideration in the radiotherapy planning:

- There is a risk of bone fracture above 60Gy, therefore when contouring a corridor of bone adjacent to CTV must be preserved to reduce fracture.
- Arm sarcomas:
 - Inmobilisation varies
 - CT problems for selected areas of the arm (upper region). If CT data does not exist the patient will have to be excluded from the trial, since this is a volume study
- Foot sarcomas:
 - CT foot as localisation
 - Try and minimise dose to sole of foot and Achilles (<=50Gy)
 - Where sole of foot is part of GTV it cannot be shielded. Where it is part of expanded CTV this may be compromised at clinician's discretion

Quality assurance

In this multi-centre randomised trial the quality assurance programme (see Appendix 6) will enable confirmation that technical guidelines within the protocol have been understood and implemented correctly by participants. The programme will ensure the dose prescription is delivered according to protocol and participants will include the appropriate documentation of technique and patient related data. This will ensure that clinical observations in terms of tumour control and normal tissue damage reflect differences in the randomised schedules rather than departures from trial protocol. Techniques used will be documented and will be available should differences in observed end points emerge.

The quality assurance programme will involve:

- a) Questionnaires, including a generic questionnaire for participant researchers new to the national trials programme and a VORTEX-specific questionnaire to be completed by all participant researchers.
- b) Volume and planning exercises to be completed by each participant researcher. The voluming exercise will be preceded by peer review and discussion at a VORTEX participant researchers meeting.

- c) Site visits to assess immobilisation techniques and delivery of dose to a site-specific tissue equivalent phantom.
- d) In-vivo dosimetry of all patients within first week of treatment.
- e) Verification of patient positioning during treatment with review of a random selection of portal images by the quality assurance team.
- f) Electronic transfer of pseudo-anonymised patient data to a central location. A random selection of these will be reviewed by the quality assurance group.

Further details can be found in Appendix 6.

Radiation treatment

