Treatment will utilize external beam megavoltage photons, and/or beams of appropriate energy to achieve required dosimetry. In general this will consist of photons in the 4/6 Mv range. Treatment will commence within 12 weeks of surgery.

Target volume

Clinical information CT scan/MRI and surgical reports will be used to determine the radiotherapy target volume.

- Gross Tumour Volume (GTV): the concept of a post-operative GTV is rarely addressed. However, the re-construction of the pre-operative GTV can be useful in planning radiotherapy treatment for this disease site. It is defined as the entire macroscopic demonstrable tumour present before surgical excision. Information about its extent should be taken from interrogation of pre-operative MRI's, clinical photos, pathology reports and operative notes.
- Clinical Target Volume I (CTV₁): comprises the GTV with a margin for suspected microscopic disease. Biopsy sites, drain sites and the surgical scar are to be included in CTV₁. CTV₁ will include a 5 cm margin to the GTV or 1 cm to the scar, whichever is longer in the cranio-caudal direction. Axially CTV₁ will be generated by adding a minimum margin of 2 cm around the GTV unless there is an intact fascial or bony boundary.

- Clinical Target Volume II (CTV₂): comprises the GTV with a reduced margin for suspected microscopic disease. No attempt will be made to encompass drain/biopsy sites or the surgical scar. CTV₂ will include a 2cm cranio-caudal margin to the GTV and an identical axial margin to CTV₁.
- Planning Target Volume (PTV): includes a margin around the CTV for inaccuracies in beam and patient set-up, and for organ and patient movement. In general a 5mm margin is considered a reasonable estimate for immobilised patients and 1cm for non-immobilised patients.

Dose prescription

All doses will be prescribed as target absorbed doses according to ICRU guidelines. The dose variation should not exceed +7%/-5% within the target volumes. All fields will be treated each session.

Limiting radiation dose to critical organs

The only organs of concern in the vicinity of the radiotherapy portals are small volumes of lung and the brachial plexus in proximal extremity lesions or the small intestine in proximal lower extremity lesions. Conventional shielding should be used to minimise the dose to these organs.

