If brachial plexus is in the volume, the dose should be limited to 60 Gy with dose <2 Gy in 33#. If necessary, these patients could be excluded from the final analysis.

Beam modification devices

Dose homogeneity should be achieved by use of appropriate wedges or/and tissue compensators where indicated. Shielding may be required.

Dose distribution

A transverse cross-sectional beam dose-distribution at the central axis, the proximal, and the distal limits of the target volume, as well as coronal and saggital views, should be reviewed by the treating clinician to ensure the anatomical arrangement of isodose contours around the target volume is achieved.

Randomised Treatment Arms

Control arm: Shrinking field technique (CTV₁ followed by CTV₂)

A total of 33 fractions each of 2Gy should be given once a day for 5 days per week over 6 weeks and 3 days in week 7, totalling 66Gy. Treatment should not be given routinely at weekends. The first 50 Gy in 25 fractions will be given to CTV₁ and subsequent 16 Gy in 8 fractions will be delivered to CTV₂.

• Research arm: (CTV₂ only)

A total of 33 fractions each of 2Gy should be given once a day for 5 days per week over 6 weeks and 3 days in week 7, totalling 66Gy. Treatment should not be given routinely at weekends. The 66Gy in 33 fractions will be delivered to CTV₂ alone. No attempt will be made to include drain/biopsy sites or the surgical scar.

In the situation where a gap in treatment extends by more than 5 days, the patient should be treated as category 1 for the remainder of the treatment and will be dealt with through local protocols. Category1 should be followed by Royal College of Radiologists guidelines for management of treatment gaps.

During radiotherapy the WHO performance status, acute skin morbidity and wound assessment will be checked weekly.

Post Radiotherapy Evaluations

The aims of follow up are to detect local and or distant recurrences and to assess the treatment morbidity and its impact on limb function.

All metastatic or local recurrence should be documented and reported to the study office. The recurrence will be assessed by clinical examination at each visit and by CT or MRI where indicated.

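### The protocol permits an undefined, discretionary exclusion of randomised patients with brachial plexus in the volume from the final analysis, open to selection bias and possibly different by arm

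*Protocol*

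**What the plan says.** The rule stands in protocol section 5, under Limiting radiation dose to critical organs. It opens "If brachial plexus is in the volume, the dose should be limited to 60 Gy with dose <2 Gy in 33" fractions and ends "If necessary, these patients could be excluded from the final analysis". The section does not say which volume is meant, what makes exclusion necessary, who decides, when, or with what knowledge of arm or outcome.

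The volumes are defined under Target volume. CTV₁ "will include a 5 cm margin to the GTV or 1 cm to the scar, whichever is longer in the cranio-caudal direction", and "Biopsy sites, drain sites and the surgical scar are to be included in" it. CTV₂ "will include a 2cm cranio-caudal margin to the GTV and an identical axial margin to" CTV₁, and does not aim to cover the scar, drain or biopsy sites. The control arm receives 50 Gy to CTV₁ and then 16 Gy to CTV₂; the research arm receives 66 Gy to CTV₂ alone.

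The trial schema in section 3 places radiotherapy planning after randomisation. Section 4 admits upper-limb lesions from the medial border of the scapula outward. Section 7 stratifies by grade, surgical clearance and centre, not by site. Section 6 names no exclusion and sets the final analysis for when all patients have at least two years of follow-up.

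A second exclusion appears under Radiotherapy Planning, for arm sarcomas: "If CT data does not exist the patient will have to be excluded from the trial, since this is a volume study". No timing is given.

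**The concern.** A randomised comparison is protected by keeping every patient in the arm allocated. Here the trigger for removal is a feature of the radiotherapy plan, which is made after randomisation and is the very thing randomised. Whoever applies the rule can see the arm from the plan, and the wording leaves the decision open case by case.

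Patients with proximal upper-limb tumours and a restricted dose could plausibly differ from the rest in limb function and in local control. Removing some of them by discretion can therefore shift either primary result. For local recurrence, judged against a fixed non-inferiority margin, the shift could go either way: dropping poor-prognosis patients mainly from control makes the research arm look worse, and dropping good-prognosis patients mainly from control makes it look better.

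**Working it through.** **1. Does qualification depend on the arm?** Two readings of the volume are possible.

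| Reading | Control arm | Research arm | Same patients qualify? |
|---|---|---|---|
| Any treated volume | CTV₁ or CTV₂: 5 cm cranio-caudally, plus scar, drain and biopsy sites | CTV₂: 2 cm cranio-caudally | No. A plexus 2 to 5 cm cranio-caudally from the GTV, or near the scar or drain, qualifies only in control |
| The 66 Gy volume | CTV₂ | CTV₂ | Yes in principle, since CTV₂ has one definition |

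The dose figures bear on this. Tissue in CTV₁ but outside CTV₂ is prescribed 50 Gy. At the protocol's upper tolerance of +7% that is 50 × 1.07 = 53.5 Gy, still below the 60 Gy in the rule. Only CTV₂ is prescribed a dose above it. This favours the second reading, but the text does not adopt it.

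**2. Is the exclusion open to bias on both readings?** Yes. On either one the removal follows randomisation, is optional, and is decided with the arm visible.

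**3. The plan's own figures.** Non-inferiority in section 6: 80% in both arms, margin 10 points, one-sided 5%, 80% power.

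n = (1.645 + 0.842)² × 2 × 0.8 × 0.2 / 0.10² = 198 per arm, as stated.

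At 200 per arm, power = Φ(0.10 / √(0.16/200 + 0.16/200) − 1.645) = Φ(0.855) = 80.4%.

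For TESS, 105 per arm gives 95.0% power by the noncentral t distribution, as stated.

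**4. Loss of patients alone.** The documents do not give the share of patients with plexus in the volume, so the shares below are assumptions. The formula is the same, with unequal arms.

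| Excluded, control / research | Remaining | Non-inferiority power |
|---|---|---|
| 2% / 1% | 196 / 198 | 79.9% |
| 5% / 2% | 190 / 196 | 79.1% |
| 10% / 4% | 180 / 192 | 77.8% |
| 5% / 5% | 190 / 190 | 78.6% |
| 10% / 10% | 180 / 180 | 76.6% |

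TESS power stays above 99% throughout.

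**5. Selection effect.** Assume the arms are truly equal at 80%, that the affected patients form the same share of both arms (the control percentage), and that their true relapse-free rate is s. All of them are removed from control and only the research percentage from research. The rate left in an arm after removing share q is (0.80 − q·s)/(1 − q).

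Example at 10%/4% with s = 0.50: control (0.80 − 0.05)/0.90 = 0.833; research (0.80 − 0.02)/0.96 = 0.8125; spurious difference 2.1 points.

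| Excluded, control / research | Spurious difference, s = 0.70 to 0.50 | Non-inferiority power |
|---|---|---|
| 2% / 1% | 0.1 to 0.3 points | 79% to 78% |
| 5% / 2% | 0.3 to 1.0 points | 77% to 73% |
| 10% / 4% | 0.7 to 2.1 points | 74% to 64% |

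The sign reverses if the excluded patients do better than the rest.

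For TESS, if affected patients score d points lower, the shift is d × (q control − q research)/(1 − q research). It runs from 10 × 0.01/0.99 = 0.1 to 20 × 0.06/0.96 = 1.25 points, against a target difference of 10.

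**The case against.** The best case against is that the sentence is permissive, that section 6 describes the primary analysis without it, and that analysis sets are commonly defined in an SAP, which is not at hand. This tempers the point. It does not remove it, because the protocol grants the permission in terms and nothing in it withdraws it.

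Several stronger readings are tempting but not supported:

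- **That the exclusion necessarily differs by arm.** This holds only if CTV₁ counts as the volume. The 50 Gy prescription to CTV₁ alone, set against the 60 Gy limit, makes the other reading at least as natural.
- **That the harm could not be undone.** The rule removes patients from the analysis, not from follow-up. The follow-up schedule makes no exception for them, and section 13 continues data collection after withdrawal from treatment unless the patient specifies otherwise. Restoring them to the analysis reverses the exclusion.
- **That a large, one-sided loss is to be expected.** No count can be derived. Even an assumed loss of 15 control patients and no research patients (185 against 200) leaves about 79.0% power against 80.4%.
- **That those deciding will have seen outcomes.** The protocol does not say who decides, and it sends interim outcome data to an independent committee.
- **That the CT-data rule is a second arm-dependent exclusion.** It has no stated timing, may be meant as an eligibility screen, and nothing links CT availability to arm.

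**Conclusion.** The point stands as a matter of validity. The protocol permits a post-randomisation exclusion that is discretionary, undefined and made with allocation known, and both primary comparisons are exposed. Dependence on arm is possible but not established, because the text leaves the volume undefined.

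The effect is probably small if only a few per cent of patients are concerned: under 1 point on the relapse-free rate at 5%/2% or less, and about 2 points at the most unfavourable combination examined. These figures rest on assumed exclusion shares and assumed outcomes among the excluded, neither of which the documents give. They also use the sample-size formula for proportions rather than the hazard-ratio analysis that section 6 specifies. No view is taken on the dose limit itself.

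**What to change.** Delete the sentence that permits exclusion from the final analysis. State in section 6 that all randomised patients are analysed in their allocated arm for both primary outcomes.

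If the team wants to see the effect of plexus cases, make it a sensitivity analysis with an arm-independent criterion, for example plexus within CTV₂, applied by someone blind to allocation and outcome. CTV₂ is drawn in both arms, so no extra contouring is needed; a criterion based on CTV₁ would require drawing that volume additionally in research-arm patients. CTV₂ is itself contoured after randomisation, which is why this belongs in a sensitivity analysis only.

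As a secondary point, say that the CT-data exclusion applies before randomisation by adding it to the eligibility check, and keep in the analysis any patient found unplannable afterwards.

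The cost is a few sentences of wording, plus a blinded review of the upper-limb plans if the sensitivity analysis is kept. No patients are added: 200 per arm retains 80.4% power for non-inferiority.

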3. STUDY DESIGN

Type of Design

This is a prospective phase III, multicentre, randomised controlled clinical trial.

Patients will be required to give informed consent twice: at registration and randomisation.

Patients will be registered into the trial prior to surgery, in order to have the initial assessments and to have the option to take part in the VORTEX-BIOBANK sub-study.

Patients will be randomised into the trial after surgery, once it has been confirmed that they are still eligible for radiotherapy treatment and the treatment options have been explained to them by a consultant oncologist/radiotherapist.

Patients must be randomised within a time frame so that trial treatment will commence within 12 weeks of surgery.

Trial Schema

Biopsy Assessment of extent of tumour by imaging

* Patient registration and completion of pre-operative TESS questionnaire

Wide local excision of sarcoma

Wound healing and assessment

Oncology appointment post-operation

*Randomisation

Stratified by: tumour grade, adequacy of definitive surgical clearance and centre

Radiotherapy planning

Control Arm Conventional two-phase treatment

Total dose: 66Gy in 33#							
Weeks 1-5: 2Gy x 5 days Weekly	CTV ₁ : 5cm margin to GTV or 1cm to the scar, whichever is longer in the cranio-caudal direction and minimum margin of 2cm axially						
Week 6 2Gy x 5 days	CTV ₂ 2 cm cranio- caudal margin to						
Week 7	GTV and minimum margin						

Research Arm Single-phase treatment to CTV₂ only Total dose: 66Gy in 33#

Weeks 1-6: 2Gy x 5 days Weekly	CTV ₂ 2 cm cranio- caudal margin to GTV and minimum margin of 2cm axially
Week 7 2Gy x 3 days	

minimum margin

of 2cm axially

CTV: Clinical Target Volume

2Gy x 3 days

^{*}Patient Registration and TESS completion after written informed consent obtained

^{**} Patient to be randomised in order for protocol treatment (radiotherapy) to begin within 12 weeks of surgery

Schedule of Events

VorteX	Pre-op	Surgery	Post-op Assessment Upon Discharge ◆	Post-op Oncology Appointment ••	RT treatment: weekly during Weeks 1-7	3 months post-op	6 months post-op	9 months post-op	12 months post-op	15 months post-op	18 months post-op	21 months post-op	24 months post-op	6 monthly Follow-up (24 months to 5 years)	Annual Follow-up (5 Years onwards)
WHO Performance Status	Χ	-	-	-	Χ	Χ	Х	X	Χ	X	X	X	Χ	X	X
Acute Skin Morbidity Assessment	-	-	-	-	X	ı	-	-	-	-	-	-	-	-	-
Wound Assessment	-	-	X	X	X	X	Х	-		-	-	-		-	-

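### The protocol permits a discretionary exclusion from the final analysis, after randomisation, of patients with brachial plexus in the radiotherapy volume

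*Protocol*

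**What the plan says.** Under the heading on limiting dose to critical organs, section 5 of the protocol states: "If brachial plexus is in the volume, the dose should be limited to 60 Gy with dose <2 Gy in 33" fractions. The next sentence is: "If necessary, these patients could be excluded from the final analysis".

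The volumes are defined earlier in section 5. For the larger one, "Biopsy sites, drain sites and the surgical scar are to be included in CTV₁", with a cranio-caudal margin of 5 cm to the GTV or 1 cm to the scar, whichever is longer. For the smaller one, "CTV₂ will include a 2cm cranio-caudal margin to the GTV and an identical axial margin to CTV₁".

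The arms differ in which volumes they treat. In control, "The first 50 Gy in 25 fractions will be given to CTV₁ and subsequent 16 Gy in 8 fractions will be delivered to CTV₂". In the research arm, "The 66Gy in 33 fractions will be delivered to CTV₂ alone".

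The trial schema in section 3 shows randomisation ("Stratified by: tumour grade, adequacy of definitive surgical clearance and centre") and then radiotherapy planning. Section 4 admits upper-limb lesions as proximal as the medial border of the scapula, so patients whose volume reaches the plexus can be randomised. Section 6 describes the primary analysis and excludes nobody.

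**The concern.** Whether the plexus lies in the volume is established at planning, which follows allocation, and whoever draws the plan must know the arm. The protocol then allows such a patient to be left out of the final analysis on an unstated judgement of necessity. It does not require that judgement to be made without knowledge of arm or outcome.

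Both primary outcomes, TESS at two years and time to local recurrence, rest on the groups as randomised. An optional exclusion made after allocation can weaken that basis even when it is applied in good faith.

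A further question arises because irradiated volume is itself the randomised factor. If the trigger depends on which volume is treated, it may not operate equally in the two arms.

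**Working it through.** **1. The plan's own figures.** Nothing here disputes them.

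- Non-inferiority (section 6: 80% control rate, 10-point margin, one-sided 5%, 80% power): n = (1.645 + 0.842)² × 2 × 0.8 × 0.2 / 0.10² = 198 per arm, as stated.
- Hazard ratio margin: ln 0.80 / ln 0.70 = 0.626, stated as 0.63. The ratio is therefore control over research.
- TESS (difference 10, SD 20, two-sided 5%, 95% power): n = 2 × (1.960 + 1.645)² × 20² / 10² = 104 per arm, against 105 stated. This agrees to within one patient.

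**2. Which volume triggers the rule?**

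| | Plexus inside CTV₂ | Plexus inside CTV₁ only |
|---|---|---|
| Treated in | both arms | control only |
| Prescribed dose | 66 Gy in 33 fractions | 50 Gy in 25 fractions |
| Against the 60 Gy limit | exceeds it | below it, even at +7% (50 × 1.07 = 53.5 Gy) |
| Against the limit of less than 2 Gy per fraction | 2 Gy, not met | 2 Gy, not met |

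The limit is expressed over 33 fractions (60/33 = 1.82 Gy each), and only CTV₂ receives 33 fractions. Holding tissue there to 60 Gy is a departure of 60/66 − 1 = −9.1%, while the protocol also says "The dose variation should not exceed +7%/-5% within the target volumes". That conflict is the likeliest reason why exclusion might be thought necessary. It arises for the same anatomy in both arms.

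The CTV₁ reading remains possible because the volume is not named and the per-fraction limit is not met in CTV₁ either. CTV₁ extends at least 5 − 2 = 3 cm beyond CTV₂ in each cranio-caudal direction. On that reading, a plexus in this zone would qualify a control patient but not a research patient with the same anatomy.

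**3. Illustrative size.** The protocol gives no frequency of plexus involvement. The 1% and 2% below (2 or 4 of 200 per arm) are assumptions.

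*Equal loss in both arms.* Power = Φ(0.10 / √(0.16 × (1/n + 1/n)) − 1.645). With 200 per arm this is 80.4%; with 196 per arm it is 79.7%.

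*Loss in control only (CTV₁ reading).* Take 160 of 200 control patients relapse-free at two years, a true research rate of 70% (60 events in 200), and the 0.63 margin. False non-inferiority = Φ((ln ratio − ln 0.63)/SE − 1.645), where ratio = ln(control rate)/ln 0.70 and SE = √(1/control events + 1/60).

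| Control patients excluded | Control rate | Ratio | SE | False non-inferiority |
|---|---|---|---|---|
| 0 | 160/200 = 80.0% | 0.6256 | 0.2041 | 4.7% |
| 2, none relapsed | 158/198 = 79.8% | 0.6327 | 0.2041 | 5.2% |
| 2, both relapsed | 160/198 = 80.8% | 0.5974 | 0.2073 | 2.9% |
| 4, none relapsed | 156/196 = 79.6% | 0.6400 | 0.2041 | 5.8% |
| 4, all relapsed | 160/196 = 81.6% | 0.5690 | 0.2108 | 1.7% |

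The rate can move either way, depending on the relapse status of the excluded patients, which is unknown.

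*TESS.* If the excluded control patients average 10 points away from the other control patients (assumed), the arm difference shifts by 10f/(1 − f): 0.10 points at f = 1% and 0.20 points at f = 2%. The standard error of the difference is 20 × √(2/200) = 2.0 points and the target difference is 10.

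**The case against.** **Arm imbalance.** A reader might infer that the rule removes control patients and keeps research patients with identical anatomy. The document does not establish that. The 33-fraction wording points to CTV₂, which both arms treat, and tissue in CTV₁ alone is prescribed less than 60 Gy, so nothing obvious would make its exclusion necessary. This objection stands as far as it goes. The imbalance is a possibility left open by an undefined term and by the per-fraction limit.

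**Direction of bias.** A reader might also infer that dropping such patients hides part of the functional benefit of the smaller volume. That is not supported either. Plexopathy is listed among events with an incidence of 5% or less, and no functional loss is shown at the dose that CTV₁-only tissue receives.

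**Permissive wording and the SAP.** The sentence mandates nothing, a decision based on anatomy and blind to arm is compatible with it, and analysis sets are commonly defined in a SAP, which is not at hand. It is therefore no fault that the protocol lacks a population definition. What remains is that the protocol expressly grants a permission to exclude after randomisation, and no other section withdraws it.

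**Size.** The illustrated effects are small and depend on assumed frequencies. That also stands, and it sets the severity.

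**Conclusion.** The point holds in a limited form. The protocol permits randomised patients to be left out of the final analysis at discretion, on a feature identified at planning after allocation, with no safeguard against knowledge of arm or outcome. On the more natural CTV₂ reading, the same anatomy qualifies in both arms and the remaining fault is the open discretion. On the CTV₁ reading, the exclusion could also fall on control patients only.

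Few patients are probably affected, but the protocol gives no number, and neither the size nor the direction of bias can be derived from it. The 1.7% to 5.8% range is an extreme for up to four exclusions, all in control and either all or none relapsed; it is not an estimate. Severity: minor.

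**What to change.** Delete the sentence that allows exclusion, and state that these patients stay in the primary analysis in the arm to which they were randomised. If their influence is of interest, permit their exclusion only as a sensitivity analysis, using one arm-neutral anatomical criterion (brachial plexus within CTV₂) applied to both arms.

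The wording of the plexus dose limit, and how it sits with the dose tolerance, can be left to the clinical planning guidelines that Appendix 6 provides for.

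The cost is one deleted sentence and a short statement on analysis. CTV₂ is treated in both arms and so is already outlined for every patient, and Appendix 6 has the planning data transferred centrally. No new patients, assessments or data are needed. Under section 13, even patients who withdraw from trial treatment remain in data collection unless they specify otherwise, so outcome data should be available for these patients too.
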